5.2.3 Indoximod /Placebo Dose Modifications (toxicity related)

Should a patient experience a Grade 3 toxicity that is possibly, probably, or definitely related to the study drug as determined by the treating investigator, the study drug will be held.

- If the toxicity resolves to Grade 2 or less within 7 days, the study drug may be resumed. If the toxicity recurs the event will count toward the early study stopping rule for excessive toxicity (section 12.2).
- If the toxicity does not improve to a grade 2 or less within 7 days or recurs, the patient will be permanently discontinued from treatment and the event will count toward the early study stopping rule for excessive toxicity (section 12.2).

If the patient experiences any Grade 4 toxicity, the study drug will be stopped and the event will count toward the early study stopping rule for excessive toxicity (section 12.2). If all toxicities resolved to Grade 2 or less, resumption of the study drug may be considered but must be discussed and agreed to by the investigator and Principal Investigator ([name]).

5.2.4 Dosing Delays/Missed Doses (non-toxicity related)

If a dose is delayed or missed for reasons unrelated to toxicity issues (i.e. patient forgets, social or employment issues, holidays, unrelated inter-current illness), the patient will be instructed to take the dose as soon as possible. If more than 6 hours from the planned dosing time has passed, the dose will be skipped. The patient will resume his usual dosing schedule with the next dose. Patients must report missed doses on the provided dose tracking sheet.

5.3 Supportive Care

Optimal supportive care will be provided for all participants.

5.4 Duration of Indoximod/Placebo

Indoximod/placebo will continue twice daily for 24 weeks unless any one of the following occurs:

- Treatment related toxicity results in a discontinuation of indoximod /placebo for more than 7 days or a toxicity recurs despite delay
- indoximod/placebo is discontinued for more than 4 weeks for any reason
- The patient is non-compliant or withdraws consent

- Disease progression occurs, although the intent is to treat all patients for a minimum of 12 weeks with indoximod/placebo before declaring progression. In addition, treatment will not be discontinued solely based on early PSA progression in the absence of clinical or definite radiologic progression.
- Inter-current illness interferes with study drug administration
- Unacceptable adverse events
- The treating investigator or Principal Investigator feels the patient's continuing participation is not in the best interest of the patient

5.5 Duration of Study Participation

Patients who begin indoximod/placebo will be followed for disease response until progression and then survival only for 2 years from study enrollment.

6 Clinical Evaluations and Procedures

Scheduled evaluations may be performed +/-3 days from the targeted date to allow for holidays and other scheduling conflicts. The final post treatment visit may be performed +/- 2 weeks. Follow-up visits may be performed +/- 4 weeks. In addition, targeted days may be altered as clinically appropriate.

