The data obtained from the Phase 1 studies performed under IND78060 suggest that certain patients with a history of exposure to targeted biologics involving components of the IDO pathway may be adversely impacted following administration of indoximod. However, these same patients were observed to have a clinical response after management of the toxicity. Therefore, the combination of indoximod with biologic agents including ipilimumab is being carefully evaluated in the clinical trial setting as described above.

The drug has not shown evidence of significant drug interactions. It is now being systematically tested in combination with docetaxel for metastatic breast cancer, in combination with ipilimumab for metastatic melanoma, in combination with temozolomide for glioblastoma, and in combination with gemcitabine/nabpaclitaxel for metastatic pancreas cancer in clinical trials under IND78189 and IND120813.

Based on phase I testing no serious toxicity is anticipated. Therefore, no specific supportive care measures are expected to be required for the drug administration itself; however dose withholding will occur for Grade 3 and 4 treatment related toxicity per section 5.2.3. Unexpected adverse events will be treated as medically indicated by the involved physicians.

Specific attention to development of autoimmune events or activation of latent infections will be given as trials using other immune-modulatory agents such as CTLA-4 blocking antibodies have shown a correlation between disease responses and so called autoimmune breakthrough events (ABEs) like hypophysitis, colitis, autoimmune hepatitis, or dermatitis. It is for this reason that they are distinguished from other adverse events. When used immediately post sipuleucel-T as in this clinical trial, it might increase the side effects of cytokine release from last infusion of sipuleucel-T. Refer to section 6.2 for study specific monitoring. Section 5.2.2 provides management of selected events.

Placebo

Placebo is a look-alike capsule containing no active ingredients and therefore no serious side effects are expected.

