6.1 Baseline and Post Treatment

Study	baseline	Weeks 0-28	Post rx visit	F/U
Evaluation	Prior to 1 st leukapheresis	Refer to table in 6.2	4 weeks after last dose of indoximod /placebo	Every 3 months from post-rx visit until 2 years from enrollment ⁸
Consent	X			
Medical history	X			
Physical exam	X			
Assessment of symptoms and analgesic needs	X		X	X
Weight	X		X	
Vital signs	X		X	
ECOG PS	X		X	
CBC/diff/plt, CD4 count	X		X	
Bun/creatinine, Na, K, Ca, Mg, tot. bili, AST, ALT, alkaline phosphatase, LDH, albumin, total protein	X		X	
Circulating Tumor Cells (CTCs)	X			
PT/INR, CPK	X			
Urinalysis ¹	X			
Testosterone	X		X	
HIV 1 & 2, hepatitis B, Hepatitis C, HTLV-1	X			
β-HCG	X			
ESR	X			
EKG	X			
CT of chest, abd, pelvis	X			X
Bone scan	X			X
PSA	X			X
Research Related				
FACT-P questionnaire	X		X	
TSH, Free T4, LH, FSH, ACTH, Cortisol ⁴	X			
Toxoplasma Ab titer	X		X ⁵	
Rheumatoid Factor	X			
C-Reactive Protein	X			
ANA panel ³ and auto-immune symptom checklist (app IV)	X			
C3, C4, CH50	X			
Samples for immune monitoring, K/T ratio and indoximod level (9 – 10 ml green tops, 1-10 ml red top)	X, X ⁶			
immune response biomarker (1-10 ml red top)	X			
Optional bx ⁷	X			

- 1- Proteinuria – any protein ≥ 2+ on dipstick or new urine active sediment/EOS should be evaluated per section 5.2.2
- 2- Toxoplasma serology positive patients will be offered prophylaxis with Septra DS per section 5.2.2
- 3- Refer to section 5.2.2 for positive ANA panel or symptoms of an autoimmune condition
- 4- Refer to section 5.2.2 for TSH > 5 or evidence of hypopituitarism
- 5- Retest sero-negative patients per section 5.2.2
- 6- Two separate sets of baseline samples to be done (i.e. at screening and prior to 1st sipuleucel-T infusion)
- 7- Biopsy for immune response biomarker only for those who provided additional consent within the treatment consent
- 8- Once disease progression is confirmed follow for survival status only

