8.2 Adverse Event Documentation

Monitoring for adverse events will begin with the signing of the consent and continue through the final treatment visit approximately 30 days after the last dose of indoximod/placebo.

For the purposes of this study, adverse event documentation requirements will be determined based on grade, expectedness and relationship to study therapy as follows:

	Grade 1	Grade 2		Grade 3		Grade 4 and 5
	Expected or Unexpected	Expected	Unexpected	Expected	Unexpected	Expected or Unexpected
Unrelated Unlikely	Not required	Not required	Not required	Not required	Required	Required
Possible Probable Definite	Not required	Not required	Required	Required*	Required*	Required*

*any grade 3 treatment related event that does not resolve to a grade 2 or better within 7 days and any grade 4 and 5 events will be considered excess and count toward an early termination event per section 12.2. Such events must be reported on the early study stopping event form found in OnCore.

In addition, although not always a reportable event, deaths (date and cause) will be recorded in OnCore upon knowledge in the follow-up tab.

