8.3 Required Reporting: Affiliates to the Masonic Cancer Center

Beginning with the signing of the consent and continuing through the final treatment visit, affiliate institutions will report all events meeting the definition of serious, regardless of attribution or expectedness, within 24 hours of knowledge of the event to the University of Minnesota Study Coordinator. After the final treatment visit, the investigator is obligated, upon knowledge of, to report any event that meets the definition of serious or life-threatening and is felt to be at least possibly related to the study drugs.

Reports are to be submitted to the Study Coordinator at the University of Minnesota Masonic Cancer Center (MCC) using the SAE reporting form found OnCore. The MCC Study Coordinator will facilitate reporting to the University Of Minnesota IRB and the FDA as required.

Affiliate institutions will be responsible for submitting reportable events to their institutional IRB and any other required local regulatory entities.

8.4 U of MN Required Reporting: FDA, IRB, MCC's SAE Coordinator, NewLink and Dendreon

The reporting period for this study is from initiation of any study treatment through the final treatment visit approximately 30 days after the last dose of indoximod/placebo; however after this point, the investigator must report upon knowledge any study treatment related event meeting the expedited reporting criteria below.

Agency	Criteria for reporting	Timeframe	Form to Use	Submission address/ fax numbers	Copy to:
U of MN IRB	Events requiring prompt reporting including, but not limited to unanticipated death of a locally enrolled subject(s); new or increased risk; any adverse event that require a change to the protocol or consent form or any protocol deviation that resulting in harm refer to http://www.research.umn.edu/irb/guidance/ae.html#.VC7xral0-sh	within 5 business days of discovery	Report Form	[contact]	MCC SAE Coordinator [contact]
FDA	Unexpected and fatal or life threatening suspected adverse reaction	As soon as possible but no later than 7 Calendar-Day	UMCC SAE	Submit as an amendment to IND with a copy to all participating affiliate institutions, Dendreon, and NewLink	

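### Routine adverse event collection ends at a visit that may fall anywhere from day 14 to day 42 after the last dose, although about 30 days is intended

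*Combined protocol and SAP*

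**What the plan says.** Section 8.2 has AE monitoring start at consent and "continue through the final treatment visit approximately 30 days after the last dose of indoximod/placebo". Section 8.3 uses the same end point for SAE reports from affiliates: "Beginning with the signing of the consent and continuing through the final treatment visit". Section 8.4 defines the reporting period as "from initiation of any study treatment through the final treatment visit approximately 30 days after the last dose of indoximod/placebo", and its table ends SAE reporting to the two companies at the final treatment visit.

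Table 6.1 schedules the post-treatment visit "4 weeks after last dose of indoximod /placebo". The opening of section 6 gives most evaluations a window of 3 days either way but treats this visit separately: "The final post treatment visit may be performed +/- 2 weeks". It then adds: "In addition, targeted days may be altered as clinically appropriate".

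After the visit, section 8.3 requires a report only of serious or life-threatening events thought at least possibly related, once the investigator learns of them. Section 8.4 makes similar provision for treatment-related events that meet the expedited criteria. Section 8.2 also has deaths, with date and cause, recorded whenever they become known.

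On autoimmune events, section 5.2.1 states: "Specific attention to development of autoimmune events or activation of latent infections will be given". Section 5.2.2 ties the symptom checklist to the section 6.2 schedule and says ANA is drawn every four weeks. Table 6.2 lists both at weeks 6, 8, 10, 14, 20 and 28. Table 6.1 marks them at baseline only.

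**The concern.** The safety follow-up period is described in days but ends at a visit, and that visit has a wide window. Two men handled exactly as the protocol allows can have different lengths of follow-up, and one of them can have about half the intended period.

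Safety is a secondary objective and endpoint in a trial of about 50 men. The section 12.2 boundary is small: 3 events in the first 5 men, 4 in the first 15, or 5 at any time. A qualifying event that starts after an early visit may never be recorded, so the length of collection should not depend on when an appointment could be made.

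**Working it through.** **Is it the same visit?** The documents call it the final post treatment visit (section 6), the post-treatment visit (table 6.1) and the final treatment visit (sections 8.2 to 8.4). The timing matches: 4 × 7 = 28 days, within 2 days of the stated 30. Section 5.2.2 also rechecks toxoplasma titers in seronegative men at the final treatment visit, and table 6.1 marks that recheck in the post-treatment column. I treat them as one visit.

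**Range of the end of collection**
- Target: 4 weeks = 28 days (table 6.1). Window: 2 weeks = 14 days (section 6).
- Earliest: 28 − 14 = day 14. Latest: 28 + 14 = day 42.
- Against 30 days: 14 − 30 = −16 and 42 − 30 = +12.
- Share of the intended period lost at the earliest visit: (30 − 14)/30 = 53%.
- Ratio of the extremes: 42/14 = 3.
- If the window were centred on day 30 instead: day 16 to day 44.
- Under the general 3-day window: day 25 to day 31. The spread therefore comes from the special window for this visit.

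The clause that lets target days move for clinical reasons has no stated limit, so day 14 to day 42 is the range from the explicit window only.

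**What an early visit leaves out**

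| Event starting after the visit | If collection were still open (8.2, 8.3) | Once the visit has closed it |
|---|---|---|
| Related, grade 2, unexpected, not serious | documented | not required |
| Related, grade 3, not serious | documented; counts under 12.2 if not down to grade 2 within 7 days | not required |
| Unrelated, serious, not fatal | reported by affiliates | not required |
| Related, serious or life-threatening | reported | still reported, on knowledge |
| Death | recorded | still recorded, on knowledge |

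The second row matters most, because it removes an event that section 12.2 counts.

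**Autoimmune schedule.** The checks in table 6.2 at weeks 6, 8, 10, 14, 20 and 28 are 2, 2, 4, 6 and 8 weeks apart. The last two gaps exceed the four-weekly ANA in section 5.2.2. The post-treatment column of table 6.1 has no checklist, ANA, thyroid or pituitary tests.

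**The case against.** The best defence is that the target is sound: 28 days is a fair rendering of about 30. The window is symmetric, so it lengthens follow-up as readily as it shortens it, and nothing in the documents suggests that visits will cluster at day 14. This stands. The threefold ratio compares the limits of what is allowed and does not predict what will happen.

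A reader might infer that grade 5 events are lost. They are not: deaths are recorded on knowledge, and survival is followed to 2 years from enrollment. Nor is it settled that unrelated grade 4 events drop out of the stopping rule. Section 12.2 and the footnote in section 8.2 refer to any grade 4 and 5 events, but the asterisk in the 8.2 table appears only in the related row. The point about related grade 3 events holds on either reading.

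A reader might also add the 8-week gap before week 28 to the 4 weeks off drug and infer 12 weeks without assessment. The documents do not support that. Week 24 has a physical examination, side-effect review, blood count, chemistry and urinalysis. The post-treatment visit has symptom assessment, blood count and chemistry. Men who complete treatment have a full check at week 28. Only the dedicated autoimmune items are missing, and mainly for men who stop between checks. Because section 5.2.2 promises the checklist only on the section 6.2 schedule, its absence after treatment is an omission and not a contradiction. The ANA frequency is a real mismatch.

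Finally, a reader might infer that the comparison between arms is biased toward no difference. That would need unequal early stopping, for which the documents give no basis. Men who stop for suspected autoimmune toxicity get an extra work-up, which could act in the other direction. Section 12 also specifies no between-arm test of adverse events.

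**Conclusion.** The point holds in a limited form. The protocol allows routine collection to close between day 14 and day 42 after the last dose, up to 16 days short of the intended 30. What can be lost is non-serious events, including related grade 3 events that would count under section 12.2, and unrelated non-fatal serious events. Deaths and related serious events remain covered.

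This assumes that the three visit names mean one visit and that only the explicit window is used. The documents do not show how many men would be seen early or how many events would start in the lost days, so the number of missed events cannot be estimated. With a stopping boundary of 5 events for the whole study, one missed event could matter, but I do not claim that one would occur.

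The autoimmune matter is secondary: an unmarked item at the post-treatment visit, and an ANA frequency stated differently in section 5.2.2 and table 6.2. The change is worth making because it is cheap, not because the design fails without it.

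**What to change.** In sections 8.2, 8.3 and 8.4, define the end of AE and SAE collection as 30 days after the last dose or the final treatment visit, whichever is later. Where the visit falls before day 30, add a short telephone contact at day 30. Alternatively, change the visit window in section 6 to 0/+2 weeks, giving day 28 to day 42. The first option is firmer, because the clause on altering target days could still move the visit under the second. Use one name for the visit throughout.

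Separately, reconcile the ANA frequency in section 5.2.2 with table 6.2, and state whether the blank autoimmune entries in the post-treatment column of table 6.1 are intended. The testing schedule itself is for the clinical team to decide.

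The cost is amendment wording and a brief call for men seen early.

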6.1 Baseline and Post Treatment

Study	baseline	Weeks 0-28	Post rx visit	F/U
Evaluation	Prior to 1 st leukapheresis	Refer to table in 6.2	4 weeks after last dose of indoximod /placebo	Every 3 months from post-rx visit until 2 years from enrollment ⁸
Consent	X			
Medical history	X			
Physical exam	X			
Assessment of symptoms and analgesic needs	X		X	X
Weight	X		X	
Vital signs	X		X	
ECOG PS	X		X	
CBC/diff/plt, CD4 count	X		X	
Bun/creatinine, Na, K, Ca, Mg, tot. bili, AST, ALT, alkaline phosphatase, LDH, albumin, total protein	X		X	
Circulating Tumor Cells (CTCs)	X			
PT/INR, CPK	X			
Urinalysis ¹	X			
Testosterone	X		X	
HIV 1 & 2, hepatitis B, Hepatitis C, HTLV-1	X			
β-HCG	X			
ESR	X			
EKG	X			
CT of chest, abd, pelvis	X			X
Bone scan	X			X
PSA	X			X
Research Related				
FACT-P questionnaire	X		X	
TSH, Free T4, LH, FSH, ACTH, Cortisol ⁴	X			
Toxoplasma Ab titer	X		X ⁵	
Rheumatoid Factor	X			
C-Reactive Protein	X			
ANA panel ³ and auto-immune symptom checklist (app IV)	X			
C3, C4, CH50	X			
Samples for immune monitoring, K/T ratio and indoximod level (9 – 10 ml green tops, 1-10 ml red top)	X, X ⁶			
immune response biomarker (1-10 ml red top)	X			
Optional bx ⁷	X			

- 1- Proteinuria – any protein ≥ 2+ on dipstick or new urine active sediment/EOS should be evaluated per section 5.2.2
- 2- Toxoplasma serology positive patients will be offered prophylaxis with Septra DS per section 5.2.2
- 3- Refer to section 5.2.2 for positive ANA panel or symptoms of an autoimmune condition
- 4- Refer to section 5.2.2 for TSH > 5 or evidence of hypopituitarism
- 5- Retest sero-negative patients per section 5.2.2
- 6- Two separate sets of baseline samples to be done (i.e. at screening and prior to 1st sipuleucel-T infusion)
- 7- Biopsy for immune response biomarker only for those who provided additional consent within the treatment consent
- 8- Once disease progression is confirmed follow for survival status only

6.2 During Treatment

Treatment	Week	Standard of Care			Research funded lab work to be performed by local (institutional) lab	Research Related Samples	indoximod / placebo count
Leukapheresis followed by sipuleucel-T infusion	0						
	1						
Leukapheresis followed by sipuleucel-T infusion	2						
	3						
Leukapheresis followed by sipuleucel-T infusion, start indoximod /placebo day after infusion	4	Prior to indoximod /placebo Physical exam, FACT-P				9 – 10 cc green, 1 – 10 cc red (pre indoximod/ placebo)	
indoximod /placebo twice daily continuously for 6 months	5						
	6	PE, review of side effects		CBC/diff/plt, chem ¹ , U/A ²	Thyroid function, C-reactive protein, ANA panel, Auto-immune symptom list	9 – 10 cc green, 1 – 10 cc red	Reconcile Drug
	7						
	8	PE, review of side effects, FACT-P	PSA	CBC/diff/plt, chem ¹ , U/A ²	Thyroid function, C-reactive protein, ANA panel, Auto-immune symptom list		Reconcile Drug
	9						
	10	PE, review of side effects		CBC/diff/plt, chem ¹ , U/A ²	Thyroid function, C-reactive protein, ANA panel, Auto-immune symptom list	9 – 10 cc green, 1 – 10 cc red	Reconcile Drug
	11-13						
	14	PE, review of side effects, FACT-P	PSA, CT of chest, abd, pelvis, bone scan	CBC/diff/plt, chem ¹ , CTCs ³ , U/A ²	Thyroid function, C-reactive protein, ANA panel, Auto-immune symptom list	9 – 10 cc green, 2 – 10 cc red, opt biopsy	Reconcile Drug
	15-19						
	20	PE, review of side effects, FACT-P	PSA	CBC/diff/plt, chem ¹ , U/A ²	Thyroid function, C-reactive protein, ANA panel, Auto-immune symptom list		Reconcile Drug
	21-23						
	24	PE, review of side effects		CBC/diff/plt, chem ¹ , protein, U/A ²			Reconcile Drug
	25-27						
28	PE, review of side effects, FACT-P	PSA, CT of chest, abd, pelvis, bone scan,	CBC/diff/plt, chem ¹ , U/A ²	Thyroid function, C-reactive protein, ANA panel, Auto-immune symptom list	9 – 10 cc green, 1 – 10 cc red	Final Reconcile Drug	

1- chem to include Bun/creatinine, Na, K, Ca, Mg, tot. bili, AST, ALT, alkaline phosphatase, LDH, albumin, total protein

2- Proteinuria – any protein ≥ 2+ on dipstick or new urine active sediment/EOS should be evaluated per section 5.2.2

3- CTCs - circulating tumor cells

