Seventeen patients with advanced/metastatic solid tumors having progressed on established salvage therapy have been studied in phase I clinical trial at dose escalating from 200 mg once daily to 600 mg twice daily continued till disease progression or 3 months with 3 patients treated

at each dose level. Pharmacokinetics for 1-MT has been linear within this dose range (7). This has been well tolerated in the patient groups so far and most patients had only grade I or II toxicities consistent with advanced disease in a heavily pretreated population (7). The most frequently reported adverse events (regardless of attribution), occurring in $\geq 30\%$ of patients, were fatigue, nausea and dyspnea (shortness of breath), muscle weakness (lower extremities), and pain in the lower extremities. The most frequently reported laboratory abnormalities (regardless of attribution), occurring in $\geq 30\%$ of patients, were lymphopenia, anemia, hypoalbuminemia, hyperglycemia, hypokalemia, and hyponatremia. In the higher dose cohorts two cases of mild hypophysitis were noted during therapy with D-1MT which resolved on its own without any pharmacologic intervention. The most frequently observed adverse event which is possibly related to D-1MT is muscle weakness of the lower extremities (25%). Lymphopenia (43.75%) is the most frequently observed laboratory abnormality possibly related to 1-MT. There have been two CTCAE grade 3 adverse events of hyponatremia and dizziness which were possibly related to 1-MT were reported.

In a separate phase I dose-escalation study, 48 patients have been treated to a maximal dose of 2000 mg bid without attaining a MTD (7). The pharmacokinetics on this study was very similar to the earlier phase I study except that AUC values did not show a proportional increase with dose at the highest dose. This is in line with experience in rats and dogs where plasma concentrations of drug plateau due to finite intestinal absorptive area. Based on pharmacokinetics of indoximod tested in phase I trial, a dose of 1200 mg bid has been proposed for the phase II trials. Twelve patients have been treated at this dose of 1200 mg bid or higher in the phase I clinical trial without any notable toxicity. Indoximod is currently being studied in an ongoing phase II clinical trial for patients with breast cancer at this dose of 1200 mg bid along with docetaxel.

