5.2.1 Expected Side Effects

All of the subjects in the indoximod clinical trials had at least one adverse event. The most frequently reported adverse events (regardless of attribution), occurring in $\geq 20\%$ of patients were fatigue, nausea, headache, and alopecia. The most frequently reported laboratory abnormalities (regardless of attribution), occurring in $\geq 20\%$ of patients were lymphopenia, anemia and hyperglycemia.

The most frequently observed adverse event which is possibly related to indoximod is fatigue (12%). Lymphopenia (16%) is the most frequently observed laboratory abnormality possibly related to

indoximod. The collective safety data from the clinical studies so far indicates indoximod has an acceptable safety profile and is safe for the treatment of patients with solid tumors.

Toxicities as updated with version 6 of the indoximod investigator's brochure (February 2015) are as follows:

Likely: Likely to happen to 20% or more of patients

- Fatigue or feeling tired
- Nausea
- Anorexia or loss of appetite
- Decrease in red blood cells (anemia)
- Diarrhea

Less Likely: Likely to happen to 10 to 19% of patients

- Decrease in white blood cells (neutrophils and lymphocytes)
- Abdominal pain
- Feeling short of breath or breathless (dyspnea)
- Rash
- Vomiting
- Constipation
- Decrease in platelets
- Headache
- Hair loss

Rare: Likely to happen to 1% than 10% of patients

- Dizziness
- Fever associated with low white blood cells
- Lung infection
- Increase in blood potassium, glucose, and creatinine levels
- Sleeplessness (insomnia)
- Low blood levels of sodium
- Multi-organ failure
- Low blood pressure
- Dehydration
- Ringing in ears
- Fever associated with low white blood cells (febrile neutropenia)
- Mouth Sores (Oral mucositis)
- Decrease in white blood cells

This drug is being employed in human clinical trials for solid tumors, breast cancer, melanoma, and pancreatic cancer. The profile of adverse events appears similar to that predicted for the study

subjects enrolled in these studies, e.g., a patient population with life-threatening disease. (7).

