preparation. All utensils and surfaces that come into contact with raw meats should not touch cooked or prepared food without being washed first. Produce should be washed well prior to eating. Meats should be cooked completely until they are not pink and their juices run clear.

Toxoplasmosis IgM and IgG titers will be checked at baseline and rechecked at the final treatment visit for serology negative patients. In addition, IgM anti toxoplasma titers will be checked if acute infection in serology negative patients is suspected while on study.

Proteinuria

Urine analysis will be performed every 2 weeks for 6 weeks then every 4 to 8 weeks thereafter. Any protein $\geq 2+$ on dipstick or new urine active sediment/ eosinophils should be evaluated.

Positive ANA Panel or Symptoms of an Autoimmune Condition

ANA will be drawn every four weeks. Any positive panel (> 5 times the upper limit of normal) should reflex over to a titer panel to determine the specific type. Any antibody titer > 5 times the ULN with symptoms consistent with an autoimmune condition should prompt withholding of indoximod and a rheumatologic evaluation. Also if inflammatory arthritis develops CCP and RF antibody titers will be evaluated.

TSH > 5

TSH will be monitored every 4 to 8 weeks and if it increases above a TSH of 5 a workup for autoimmune thyroiditis will be performed (anti-TG and anti-TPO Ab tests, thyroid uptake scan, FNA of the thyroid if warranted).

Also baseline and every 4 to 8 weeks, LH, FSH, ACTH, cortisol will be used to monitor for hypophysitis. These labs should be drawn between 7-8 AM due to the natural circadian variation of ACTH and cortisol. If any of these tests are lower than the reference lab values at the clinical institution and the primary investigator suspects hypopituitarism then study treatment should be held and a workup performed. This includes an MRI of the brain with attention to the sellar area to evaluate for hypophysitis.

Ophthalmologic Complaints

Any ophthalmologic complaints (including new ocular pain/inflammation, photosensitivity, or diminished vision) will be evaluated by an ophthalmologist if the treating investigator deems it necessary.

Symptoms of Myositis

CPK will be checked if any symptoms of myositis occur.

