7.6 Return/Destruction of Study Drug

At the conclusion of the study ensure that all documentation regarding receipt, storage, dispensing, return of used containers, and accountability is complete and accurate. Unused drug obtained from NewLink Genetics must be returned to NewLink or be destroyed on site using appropriate procedures upon written authorization from NewLink to do so.

8 Adverse Event Documentation and Reporting

Toxicity and adverse events will be classified according to NCI's Common Terminology Criteria for Adverse Events V 4.0 (CTCAE) and reported on the schedule below. A copy of the CTCAE can be downloaded from the CTEP home page

(http://ctep.cancer.gov/protocolDevelopment/electronic_applications/ctc.htm#ctc_40).

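### Blood glucose is in neither written-out chemistry list, so hyperglycemia, which the protocol names as a frequent laboratory abnormality, is not systematically measured

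*Combined protocol and SAP*

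**What the plan says.** Section 6.2 schedules chemistry at weeks 6, 8, 10, 14, 20, 24 and 28 and spells out the panel in footnote 1: "chem to include Bun/creatinine, Na, K, Ca, Mg, tot. bili, AST, ALT, alkaline phosphatase, LDH, albumin, total protein". The chemistry row of section 6.1, for baseline and the visit 4 weeks after the last dose, carries the same list: "Bun/creatinine, Na, K, Ca, Mg, tot. bili, AST, ALT, alkaline phosphatase, LDH, albumin, total protein". No HbA1c or named metabolic panel is scheduled elsewhere.

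The risk text mentions raised glucose three times:

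- Section 2.3, first phase I trial: the abnormalities seen in at least 30% of patients, whatever the attribution, "were lymphopenia, anemia, hypoalbuminemia, hyperglycemia, hypokalemia, and hyponatremia".
- Section 5.2.1, across indoximod trials: the abnormalities seen in at least 20% "of patients were lymphopenia, anemia and hyperglycemia", again whatever the attribution.
- Section 5.2.1, the toxicity list updated to version 6 of the investigator's brochure: "Increase in blood potassium, glucose, and creatinine levels", under the Rare heading (about 1% to 10%).

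Safety of indoximod after sipuleucel-T is a secondary objective (section 1.2). Events are graded by CTCAE v4.0 (section 8). Grade determines whether study drug is held or stopped (section 5.2.3), whether an event must be documented (section 8.2) and whether it counts toward early termination (section 12.2).

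**The concern.** The protocol names a set of laboratory abnormalities and schedules tests that cover all of them except one. Lymphocytes, neutrophils, hemoglobin and platelets come from the blood count. Albumin, sodium, potassium and creatinine come from the chemistry panel. Glucose comes from neither, and no reason is given, so this looks like an oversight.

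If sites run only the listed analytes, the trial has no glucose value before or during study drug. A low count of hyperglycemia would then partly reflect not looking. A high value found by chance could not be separated from one present before treatment, which weakens the attribution that sections 5.2.3 and 8.2 ask the investigator to make. If some sites report glucose routinely and others do not, the observed rate would also depend on where a man was treated, with up to 5 sites planned.

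**Working it through.** The plan states no figure to reproduce here, so the check is mainly a reading of the schedules.

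**1. Time points.** Baseline (1) + on-treatment visits at weeks 6, 8, 10, 14, 20, 24 and 28 (7) + post-treatment visit (1) = 9 chemistry samples. Glucose is listed at 0 of the 9.

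**2. Other scheduled assessments.**
- Section 5.2.2: "Urine analysis will be performed every 2 weeks for 6 weeks then every 4 to 8 weeks thereafter". The only action rule attached concerns protein, sediment and eosinophils. Urinalysis does not measure blood glucose, and section 6.1 does not schedule it at the post-treatment visit.
- Side-effect review takes place at all seven on-treatment visits and could identify symptomatic cases.
- The endocrine items of the Appendix IV checklist ask about cold intolerance, hair, voice and skin, not about symptoms of high glucose.

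**3. Expected number of men with hyperglycemia.** Inputs: about 50 men randomized 1:1, so n = 25 on indoximod; p is each documented rate. Expected count = n × p. The chance of at least one case in the arm, if all were measured, is 1 − (1 − p)^25.

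| Documented rate p | 25 × p | Chance of at least one case |
|---|---|---|
| 1% (low end of Rare) | 0.25 | 0.22 |
| 10% (high end of Rare) | 2.5 | 0.93 |
| 20% (section 5.2.1, all causes; stated as a minimum) | 5 | above 0.99 |
| 30% (section 2.3, all causes; stated as a minimum) | 7.5 | above 0.99 |

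The range is therefore about 0.25 to 7.5 or more.

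**4. Do the documented rates agree?** Within section 5.2.1, hyperglycemia is at 20% or more in the opening text and at about 1% to 10% in the list. A difference in attribution might explain this, but the list does not state its basis. Nor does restricting it to possibly related events obviously fit: fatigue is in the 20%-or-more group, while the text puts possibly related fatigue at 12%.

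**5. What a comparison between arms could show.** The documents give no placebo rate, so the pairs below are assumptions. Method: two-sided 0.05 normal approximation, 25 per arm, power = Φ[(|p1 − p2| − 1.96 × SE0) / SE1], with SE0 from the pooled rate and SE1 from the separate rates. For 10% vs 30%: pooled rate 0.20; SE0 = √(0.20 × 0.80 × 2/25) = 0.113; SE1 = √((0.10 × 0.90 + 0.30 × 0.70)/25) = 0.110; power = 0.42. In the same way, power is 0.16 for 10% vs 20% and 0.34 for 20% vs 40%.

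**6. What section 8.2 would capture.** Grade 1 events need no documentation. Neither do expected grade 2 events, nor expected grade 3 events judged unrelated or unlikely. Raised glucose is on the expected list, so most elevations, even if measured, could stay outside the adverse event record.

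**The case against.** A reader might infer that hyperglycemia cannot be detected, graded or compared at all in this trial. The documents do not support that. Footnote 1 says what the panel is to include, which sets a minimum; a local laboratory may report glucose anyway, and the documents do not settle whether it would. Examination, side-effect review and urinalysis take place at seven visits and could find marked or symptomatic cases. Section 8.2 requires related grade 3 events and all grade 4 and 5 events to be documented once found. All of this stands. What remains is that capture is left to chance and local habit, and that documentation rules help only after an event has been noticed.

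A reader might also take 20% to 30% as the rate to expect here. Both figures are regardless of attribution. The higher one comes from a 17-patient trial in advanced, heavily pretreated disease, whereas this trial enrols men with ECOG 0 or 1 and excludes recent systemic corticosteroids. The brochure-based list gives about 1% to 10%. The full range therefore has to be shown.

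A third tempting inference is that holds, stops or early-termination counts would be missed in some known number. No grade 3 or 4 hyperglycemia rate is given, and a grade 3 event leads to a hold only if at least possibly related, so that number cannot be derived.

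Finally, adding the analyte alone would not yield a comparison, because of section 8.2 and because section 12 plans no laboratory summary by arm. That is correct, and the fix below takes it into account.

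**Conclusion.** The point holds in this form: glucose is not a required measurement at any of the nine chemistry time points, although the protocol itself names hyperglycemia among the most frequent laboratory abnormalities. It is therefore not systematically measured, no baseline value is assured, and rates by grade could not be reliably compared between arms.

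The size depends on which documented frequency applies, and the gap exists at either end of the range. The counts assume 25 men on indoximod and that rates from other populations carry over to this one. Even with complete measurement, 25 per arm supports a description rather than a test. The primary endpoint is not affected. This is a worthwhile and inexpensive repair to the safety objective, not a flaw that undermines the trial.

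**What to change.** 1. Add glucose to footnote 1 of the table in section 6.2 and to the chemistry row of the table in section 6.1, run on the sample already drawn at the nine time points.
2. Have the glucose values recorded as data, and add to section 12 a descriptive summary by arm (baseline, change from baseline, worst grade on treatment), without a formal test. This is needed because section 8.2 leaves low-grade expected events undocumented.
3. Reconcile the hyperglycemia frequencies in sections 2.3 and 5.2.1, stating the population and the attribution basis of each.

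The cost is a minor laboratory charge, some incidental high values to grade, and a small amount of data entry and analysis. No new visit or blood draw is needed.
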